A sterile, isotonic solution that contains hyaluronan, sulfobetaine, poloxamine, boric acid, sodium borate, edetate disodium and sodium chloride and preserved with a dual disinfection system: polyaminopropyl biguanide 0.00013% and polyquaternium 0.0001%.

This will be used with a rub and rinse step.

CONTACT LENSES: The following six lens types will be used to represent a cross-section of lenses in use: ACUVUE® 2, ACUVUE® VITA® (Johnson & Johnson Vision Care), Air OPTIX® (Alcon), Biofinity®, Clariti (CooperVision), PureVision® (Bausch & Lomb)

Approximately 33 subjects will be allocated to use each lens type: 22 using the test MPS product and 11 using the control product. Each site will use four lens types.

NO. OF SITES: Approx. 10 (3-5 UK and 5-6 US) sites. Each site will enroll approx. 20 subjects.

NO. OF SUBJECTS: Total approx. 200 subjects (400 eyes), approx. 20 subjects/site. The aim is for at least 180 subjects to complete the study; 30 in each lens group (20 using the test solution and 10 using the control solution).

	Test Group	Control Group	Total Subjects
Site 1 to 10	~14	~7	~20
Total	133	67	200

STUDY POPULATION:	Volunteer subjects will be currently adapted soft contact lens wearers (>1 month of lens wear), be at least 18 years of age with contact lens sphere power requirement in the range +4.00 to -8.00D and refractive astigmatism of less than or equal to 0.75D in each eye.
VARIABLES:	
Comfort (0-10)
 
Average wearing time (WT), comfortable WT (hrs.)
 
Visual acuity (Snellen/logMAR)
 
Slit lamp findings, including corneal edema, limbal and bulbar hyperemia, vascularization, palpebral hyperemia and roughness, corneal staining, conjunctival staining, etc. (0-4)
 
Lens surface wettability (0-4)
 
Lens surface deposits (0-4, no. of spots)
 
Adverse events

IN VITRO MEASUREMENTS:	Deposit analysis in dark field illumination using a modified version of the method of Lowther et al (ICLC 1991;18:219-26) on approx. 60 lenses.
VISITS/SCHEDULE:	
There will be four scheduled visits (visit 1a and 1b may be conducted on the same day):
 
Visit 1a: Baseline
 
Visit 1b: Lens issue
 
Visit 2: 1 week follow-up (7 days \pm3 days) – WT 1-3 hours
 
Visit 3: 1 month follow-up (30 days \pm4 days)

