7.5.2 Visit 2: 1-week Follow-up

The 1-week follow-up visit will be scheduled 1 week (7 days ± 3 days) from the lens dispensing date. The subject should wear the lenses 1 to 3 hours prior to the appointment. This has been shown to be the time period when solution-induced corneal staining is most evident.⁵ If the subject attends without lenses or with more than 3 hours of lens wear on that day and they are not having any problems with their lenses or the study solution, the visit should be rescheduled, if possible within the visit window.

The following clinical test variables will be recorded on the Follow-Up Visit eCRF:

- i. Wearing times:
 - Days worn since last visit
 - Typical insertion time
 - Typical removal time
 - Typical time CL comfort deteriorates
 - Maximum wearing time since last visit (hrs.)
 - Wearing time today (hrs.)
- ii. Rewetting drop usage (type and frequency)
- iii. Symptoms, problems and complaints
- iv. Subjective assessments
 - Overall comfort on insertion, during the day and prior to removal (0-10)
- v. Vision
 - Subjective vision quality: distance (0-10 scale).
 - Monocular VA (CL, Snellen/logMAR to the nearest letter)
 - Spherical over-refraction (SOR)
 - Monocular HC DVA with SOR
 - Binocular distance VA with CLs
- vi. Lens surface characteristics
 - Lens surface wetting (0-4)
 - Lens deposits (film: 0-4, no. of white spots)
- vii. Lens fit
 - Centration (0-2)
 - Corneal coverage (Y/N)
 - Post-blink movement (0-4)
 - Tightness on push-up (0-4)
 - Overall fit acceptance (0-4) and reason if Grade 2 or less
- viii. Remove lenses and store in sterile saline
- ix. Slit lamp examination
 - Limbal hyperemia (0-4)
 - Bulbar hyperemia (0-4)
 - Stromal edema (0-4)
 - Vascularization (0-4)
 - Palpebral conjunctival hyperemia (0-4)
 - Upper palpebral roughness (0-4)
 - Corneal staining (type 0-4)
 - Conjunctival fluorescein staining by quadrant (0-4)
 - Other findings (0-4)

See Appendix 4 for grading scales and measurement instructions.

Rinse away fluorescein with non-preserved saline.

Re-insert study lenses.

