10.2 Statistical Analysis Plan

General considerations: All data summaries and statistical analyses will be performed using the SAS software Version 9.4 or higher (SAS Institute, Cary, NC). Throughout the analysis of data, the results for each subject/eye will be used when available for summarization and statistical analysis. Missing data will be excluded from the analysis. Unscheduled visits will be excluded from the statistical analysis.

Descriptive statistics will be reported by solution type at baseline, dispensing, and each follow-up visit according to ISO 11980:2012. Continuous variables will be summarized using sample size (N), mean, standard deviation (SD), minimum and maximum, and categorical data variables will be summarized using the sample size, frequency distribution (count and percentage of subjects or eyes in each category), mean, median and SD.

Analysis Population: Statistical Analysis for hypothesis testing will be performed on all evaluable subjects. All inference will be carried out with an overall type I error rate controlled at 0.05.

Analysis of comfort: Results will be analyzed using a linear mixed model including the experimental design factors: solution type, visit and their interaction will be included as fixed effect factors and site and subject as random effects.

Comparisons between the test and control solutions will be carried out using pairwise one-sided confidence intervals constructed for least-square mean differences (mean difference calculated as Test minus Control). Non-inferiority will be concluded if the lower confidence limit is greater than -1.0.

Analysis of visual acuity: Results will be analyzed using a linear mixed model including the experimental design factors: solution type, visit and their interaction will be included as fixed effect factors and site and subject as random effects.

Comparisons between the test and control solutions will be carried out using pairwise one-sided confidence intervals constructed for least-square mean differences (mean difference calculated as Test minus Control). Non-inferiority will be concluded if the upper confidence limit is less than +0.05 logMAR.

Analysis of wettability: Results will be analyzed using a linear mixed model including the experimental design factors: solution type, visit and their interaction will be included as fixed effect factors and site and subject as random effects.

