Comparisons between the test and control solutions will be carried out using pairwise one-sided confidence intervals constructed for least-square mean differences (mean difference calculated as Test minus Control). Non-inferiority will be concluded if the lower confidence limit is greater than -0.5.

Analysis of deposits: Results will be analyzed using a linear mixed model including the experimental design factors: solution type, visit and their interaction will be included as fixed effect factors and site and subject as random effects.

Comparisons between the test and control solutions will be carried out using pairwise one-sided confidence intervals constructed for least-square mean differences (mean difference calculated as Test minus Control). Non-inferiority will be concluded if the upper confidence limit is less than +0.5.

Analysis of slit lamp findings: First the results will be averaged across each sector. Average results will be analyzed using a linear mixed model including the experimental design factors: solution type, visit and their interaction will be included as fixed effect factors and site and subject as random effects.

Comparisons between the test and control solutions will be carried out using pairwise one-sided confidence intervals constructed for least-square mean differences (mean difference calculated as Test minus Control). Non-inferiority will be concluded if the upper confidence limit is less than +0.5.

Additional analyses:

- Overall occurrence of slit lamp findings of Grade 2 or higher
- Overall occurrence of lens VA findings worse than 6/12 (20/40)
- Overall occurrence of clinically significant lens surface deposits (>Grade 1)
- Ocular adverse events.

Any deviations from the above analysis will be documented in the report.

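### Section 10.2 names no eye, subject-by-visit or visit-variance structure for the eye-level primary endpoints, so non-inferiority limits taken by visit could have the wrong width

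*Combined protocol and SAP*

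**What the plan says.** Section 10.2 repeats one model for each primary endpoint: solution, visit and "their interaction will be included as fixed effect factors and site and subject as random effects". The slit lamp paragraph does the same after a pre-processing step, "First the results will be averaged across each sector". Averaging over sectors is stated; averaging over eyes is not.

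On the unit of analysis, the general considerations say that "the results for each subject/eye will be used when available for summarization and statistical analysis". The synopsis counts "Total approx. 200 subjects (400 eyes), approx. 20 subjects/site". Section 7.5.2 lists "Monocular VA (CL, Snellen/logMAR to the nearest letter", and Appendix 4 grades wetting and deposits on the lens and staining by sector of the cornea. Comfort is different: it is listed as "Overall comfort on insertion, during the day and prior to removal (0-10", with no mention of a rating per eye.

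Section 10.2 names no eye effect, subject-by-visit effect, residual covariance or separate visit variance. It does not list the visits that enter the model. It bases the decision on one-sided limits for least-squares mean differences, but does not say whether these are taken at each visit or averaged over visits.

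**The concern.** With follow-up at 1 week and 1 month, a subject can contribute four values to each eye-level endpoint. A subject intercept with a single residual variance gives every pair of those values the same correlation. Two eyes graded in one sitting are then assumed to be no more alike than the left eye at week 1 and the right eye at month 1. Fellow eyes at one visit share the day, the grader and the wear time, so this is hard to believe. The same model assumes equal spread at both visits, although the wear-time rules differ: 1 to 3 hours before Visit 2 (section 7.5.2), and at least 2 hours with no upper limit before Visit 3 (section 7.5.3).

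Non-inferiority is decided by the position of a one-sided limit. If the standard error (SE) is too small, the limit is too narrow and false non-inferiority exceeds the nominal rate. If it is too large, power is lost.

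**Working it through.** **What the documents give.** At least 180 completers and dropout below 10% yield 180/0.90 = 200 enrolled, split 2:1 as 133 and 67, which matches the plan. Completers are 120 test and 60 control. There is no power statement, SD, SE or correlation to reproduce, so every correlation and SD below is an assumption. The per-interval confidence level is not stated either; one-sided 5% (z = 1.645) is assumed.

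**Set-up.** Take four values per subject (2 eyes x 2 visits), balanced, with the site effect left out. Let r1 be the correlation of fellow eyes at the same visit, r2 the same eye across visits, and r3 different eye and different visit.

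**Equal visit variances (set to 1).**
- True variance of a subject's two-eye mean at one visit: (1 + r1)/2.
- The subject-intercept model replaces all three correlations by their mean, rbar = (r1 + r2 + r3)/3, and so uses (1 + rbar)/2.
- SE ratio (model/true) = sqrt[(1 + rbar)/(1 + r1)]. The factor (1/120 + 1/60) cancels.
- Actual one-sided error = P(Z > 1.645 x ratio).

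| r1 / r2 / r3 | Model variance | True variance | SE ratio | Error |
|---|---|---|---|---|
| 0.6 / 0.5 / 0.4 | 0.750 | 0.800 | 0.968 | 5.6% |
| 0.8 / 0.5 / 0.45 | 0.792 | 0.900 | 0.938 | 6.1% |
| 0.9 / 0.3 / 0.27 | 0.745 | 0.950 | 0.886 | 7.3% |
| 0.5 / 0.7 / 0.45 | 0.775 | 0.750 | 1.017 | 4.7% |

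**Unequal visit variances.** Let the SD be 1 at the quieter visit and s at the noisier one.
- Pooled variance T = (1 + s²)/2; mean covariance c = [r1·T + (r2 + r3)·s]/3.
- Model variance at either visit: (T + c)/2.
- True variance: s²(1 + r1)/2 at the noisier visit, (1 + r1)/2 at the quieter one.

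Example, 0.9/0.3/0.27 with s = 1.5: T = 1.625, c = 0.7725, model variance 1.199, true variance at the noisier visit 2.1375, ratio 0.749, error 10.9%.

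| r1 / r2 / r3 | Noisier visit: ratio, s = 1.25 to 1.5 | Error | Quieter visit: ratio |
|---|---|---|---|
| 0.6 / 0.5 / 0.4 | 0.875 to 0.816 | 7.5% to 9.0% | 1.093 to 1.225 |
| 0.8 / 0.5 / 0.45 | 0.847 to 0.791 | 8.2% to 9.7% | 1.059 to 1.186 |
| 0.9 / 0.3 / 0.27 | 0.801 to 0.749 | 9.4% to 10.9% | 1.001 to 1.123 |
| 0.5 / 0.7 / 0.45 | 0.918 to 0.856 | 6.6% to 8.0% | 1.147 to 1.283 |

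**Average over both visits.** The true variance of a subject's four-value mean is (4T + 12c)/16 = (T + 3c)/4. The model uses the same T and c, so the SE is right in balanced data whatever the correlations.

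**Simulation check** (20,000 trials, 120 v 60, no site effect). At 0.8/0.5/0.4 with equal variances, the error was 6.2% and 6.0% by visit (closed form 6.2%) and 4.8% for the two-visit average. With s = 1.5 it was 10.0% at the noisier visit, 2.8% at the quieter one (closed form 9.8% and 2.6%) and 5.1% for the average.

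**Size against the margins, equal variances.** The correct half-width is 1.645 x SD x sqrt[(1 + r1)/2 x 0.025], where 1/120 + 1/60 = 0.025. In the worst set (0.9/0.3/0.27) at an SD of 0.8 grade it is 0.203, against 0.180 from the model. The gap of 0.023 is 4.6% of the 0.5 margin. At an SD of 0.4 the gap is 0.012, or 2.3%. For visual acuity in the same set, SDs of 0.08 to 0.12 logMAR give gaps of 0.0023 to 0.0035, or 4.6% to 7.0% of the 0.05 margin.

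**The case against.** The strongest reply is that the plan never says non-inferiority is judged by visit. If the contrast is averaged over visits, the SE is right in balanced data and the issue disappears. This stands. The interaction term makes limits by visit a natural reading, but nothing in section 10.2 settles it.

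Four stronger conclusions are tempting, and the documents do not support them:
- *That the plan specifies a wrong model.* It is silent on residual covariance; a single residual variance is the literal reading, not a stated choice. Nor does it list the visits in the model. The defect is under-specification.
- *That the 1-week visit is the noisier one, so the error falls on the safety endpoint.* Section 7.5.2 says of the 1-to-3-hour window: "This has been shown to be the time period when solution-induced corneal staining is most evident". That concerns how visible staining is, not its spread, and covers staining only. Wear time is less tightly controlled at Visit 3, which could make that visit the noisier one.
- *That the limits are always too narrow.* When the same eye resembles itself across visits more than it resembles its fellow, they are slightly too wide.
- *That all seven endpoints share the fellow-eye problem.* Comfort appears to be one rating per subject; only the visit-variance point could apply to it.

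It is also fair to say that, with equal visit variances, the effect is small and would change a conclusion only for a limit lying close to its margin.

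**Conclusion.** The point holds as an omission with a conditional consequence. Three conditions are needed: eye-level data from Visits 2 and 3, one residual variance, and a decision taken by visit. Given these, the one-sided limits for the six eye-level endpoints have the wrong width.

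With equal visit variances the distortion is modest: a nominal 5% error becomes 4.7% to 7.3%, and the limit moves by at most about 5% of the 0.5 grade margin at SDs of 0.4 to 0.8. Visit SDs that differ by a factor of 1.25 to 1.5, in either direction, matter more: the SE is 8% to 25% too small at the noisier visit, and from about correct to 28% too large at the other.

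Confidence is high that the structure is missing and moderate on its size, because the correlations and SDs are all assumed. The change is worth making because it is cheap and settles the covariance and the deciding contrast before the data are seen.

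**What to change.** In section 10.2, for each eye-level endpoint:
- Average the two eyes per subject and visit. Fit solution, visit and their interaction with an unstructured 2 x 2 covariance over Visits 2 and 3, site as a random effect, and Kenward-Roger degrees of freedom. Take the one-sided limits from this model.
- State whether the deciding contrast is at each visit or averaged over visits.

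An alternative is to keep eye-level records and add eye-within-subject and subject-by-visit effects with visit-specific variances. With up to four values per subject on 0-4 grades this may not converge, so the averaged-eye model is the safer primary choice.

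The cost is a few sentences and a few lines of SAS, with no new data. Some limits become slightly wider.

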2.1.2 Safety Hypotheses

The Oté Sensation multi-purpose solution will be non-inferior to the Bausch & Lomb BioTrue solution in terms of:

Corneal staining – type (mean grade, 0-4), a non-inferior bound of 0.5 will be used.

Limbal hyperemia (grade, 0-4), a non-inferior bound of 0.5 will be used.

Bulbar hyperemia (grade, 0-4), a non-inferior bound of 0.5 will be used.

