 - Palpebral conjunctival hyperemia (0-4)
 - Upper palpebral roughness (0-4)
 - Corneal staining by sector (type 0-4)
 - Conjunctival fluorescein staining by quadrant (0-4)
 - Other findings (0-4)

See Appendix 4 for grading scales and measurement instructions.

- xv. Complete the eligibility checklist

If at this point the subject is found to be ineligible, then complete an Exit eCRF and exit the subject from the study.

If eligible, the subject will be assigned to one of the four lens types allocated to the site and assigned to one of the study solutions.

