Variable	Assessment Method	Grading/Measurement System
Corneal Staining Type	Assessed by sector with fluorescein, blue light, yellow filter and full beam using medium magnification. Cornea will be assessed by sector (C, N, T, I, S)	0 NONE: No staining 1 Micropunctate – Superficial, minute/fine/pinpoint punctate staining, includes superficial stippling 2 Macropunctate – Focal, ball-like punctate staining, includes moderate stipple staining 3 Coalesced macropunctate 4 Patch (> 1 mm)
Conjunctival Staining	Assessed by quadrant using fluorescein, blue light, yellow filter, low-medium magnification. Ignore conjunctival indentation with no staining.	0 None 1 Minimal diffuse punctate 2 Coalescent punctate 3 Confluent 4 Widespread confluent
Other Significant Findings	Describe finding and grade severity	0 NONE 1 TRACE 2 MILD 3 MODERATE 4 SEVERE
Lens Surface Characteristics		
Lens Surface Wetting	Lens surface wettability rated on the appearance of the lens surface and the drying time viewed with a slit lamp under low magnification.	0 VERY POOR: Immediately displaying non-wetting areas on lens surface. 1 POOR: Irregular surface appearance; drying time < interblink period. 2 ACCEPTABLE: Smooth surface appearance immediately after the blink becoming irregular with time; drying time \geq interblink period. 3 GOOD: Typical lens appearance with long drying time. 4 EXCELLENT: Appearance of a healthy cornea with very long drying time.
Film Deposits	Any film deposits (protein/lipid) attached to the front surface of the lens. Scan the entire lens surface (10- 20X) for the presence of deposits.	0 No film. 1 Slight film visible only under magnification. 2 Moderate film only under magnification. 3 Moderate film visible to the naked eye 4 Heavy film visible to the naked eye
White Spot Deposits	Assessed using slit lamp with white light, low-medium magnification	Number of white spot deposits

MEASUREMENT INSTRUCTIONS**DISTANCE VISUAL ACUITY**

Measure Visual Acuity (VA) to the nearest letter.

If the subject reads more than half of the letters on a given line, ask them to attempt the next line. Then if the subject is able to read letters on the next line assume that the previous line was correctly read for the purposes of recording VA.

EXAMPLE 1: If all six of the letters on the 6/9 line were correctly identified and the subject then correctly identified all but one of the six letters on the 6/7.5 line, record the acuity as:

6 / 7.5 - 1

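### Does averaging corneal staining over five sectors leave localised staining out of the safety comparison?

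*Combined protocol and SAP*

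**What the plan says.** Section 2.1.2 sets the staining hypothesis on an average: "Corneal staining – type (mean grade, 0-4), a non-inferior bound of 0.5 will be used". The neighbouring hyperemia hypothesis carries the same number without the word mean: "Limbal hyperemia (grade, 0-4), a non-inferior bound of 0.5 will be used". Section 7.4 and Appendix 4 have staining type graded 0 to 4 in five corneal sectors (central, nasal, temporal, inferior, superior).

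Under slit lamp findings, Section 10.2 starts with "First the results will be averaged across each sector" and continues "Average results will be analyzed using a linear mixed model including the experimental design factors". Non-inferiority requires an upper limit below +0.5.

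Two other parts of Section 10.2 bear on the point. The general considerations state "Descriptive statistics will be reported by solution type at baseline, dispensing, and each follow-up visit according to ISO 11980:2012", with counts and percentages per category for categorical variables. A separate list of additional analyses contains "Overall occurrence of slit lamp findings of Grade 2 or higher" and ocular adverse events.

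**The concern.** Staining is one of three safety non-inferiority endpoints, and Section 7.5.2 times Visit 2 to the hours of wear when solution-induced staining is said to be most evident. A rule on the five-sector mean shrinks a one-sector effect five-fold and a two-sector effect 2.5-fold. The documents do not say why 0.5 suits this averaged scale, and the same number serves hyperemia, which appears to be one grade per eye. The rule could therefore pass while the test arm had a clear excess of eyes at Grade 3, the level at which Sections 7.6 and 8.4 call for action.

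The Grade 2 or higher listing is the obvious safeguard. However, it names no unit (sector, eye or subject), no between-arm difference and no interval. If it were computed on averages, it would miss Grade 3 staining in one, two or three sectors.

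**Working it through.** **Numbers of subjects.** The synopsis aims for 30 completers in each of six lens groups, 20 test and 10 control: 6 × 30 = 180, or 120 test and 60 control. With 10% drop-out, 180 / (1 − 0.10) = 200, which matches the stated enrolment.

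**Dilution.** Grade 3 in k of five sectors averages a = 3k/5: 0.6, 1.2, 1.8, 2.4 and 3.0 for k = 1 to 5. For an excess confined to one sector to move the mean by 0.5, it must average 5 × 0.5 = 2.5 grades over all test subjects.

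**Chance that the rule passes.** The documents give no SD and no staining rates. Assumed here: Grade 3 in k sectors of 20% of test and 5% of control eyes, one eye per subject, background SD of the sector mean 0.3 or 0.5, and a one-sided 95% limit (Section 10.2 states no level).

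- d = a × (0.20 − 0.05)
- SE = √[(a² × 0.20 × 0.80 + SD²)/120 + (a² × 0.05 × 0.95 + SD²)/60]
- Expected upper limit = d + 1.645 × SE
- Pass probability = Φ[(0.5 − d)/SE − 1.645]

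| Sectors | d | SD | SE | Upper limit | Pass probability |
|---|---|---|---|---|---|
| 1 | 0.09 | 0.3 | 0.055 | 0.18 | >99.9% |
| 1 | 0.09 | 0.5 | 0.084 | 0.23 | 99.9% (0.9994) |
| 2 | 0.18 | 0.3 | 0.073 | 0.30 | 99.7% |
| 2 | 0.18 | 0.5 | 0.096 | 0.34 | 95% |

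With a one-sided 97.5% limit the pass probabilities are at least 99.8% for one sector and 91% to 99% for two. The dilution is real and does not depend on the unstated level.

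**Diffuse staining.** With a clear control arm and Grade 3 in all five sectors (a = 3), the expected upper limit reaches 0.5 once about 10% to 12% of test eyes are affected, for SD from 0.5 down to 0. The rule is sensitive to widespread staining.

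**What the planned tables would show.** On recorded grades, the 20% against 5% scenario gives 24/120 against 3/60 (assuming no other staining of Grade 2 or higher). That is a difference of 15 points, Newcombe 95% interval 4 to 24. The counts come from tables that Section 10.2 already requires by solution; the interval follows from them directly.

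**Which grades the listing counts.** The averaging sentence belongs to the mixed-model analysis, and the Grade 2 listing stands under another heading. Appendix 4 defines its categories for the recorded grade. A five-sector mean moves in steps of 0.2 and has no such categories. Counting recorded grades is the natural reading.

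**Would such an imbalance go unnoticed?** Table 4 classes other corneal findings of Grade 3 or more as significant adverse events, Section 8.2 requires them to be notified within 2 working days, and Section 7.6 lists Grade 3 or 4 findings as grounds for discontinuation. If every affected subject left, 0.20 × 133 + 0.05 × 67 = 26.6 + 3.4, or about 30 subjects, would go. That is 15% of 200, leaving about 170 completers, against a target of 180 and an assumed drop-out below 10%.

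**The case for a change.** The strongest reply is that seeing an imbalance in a table is not the same as having a pre-specified estimate of it. The non-inferiority statement is the headline, and nothing planned beside it carries a between-arm interval for localised staining. Section 10.2 also excludes missing data and unscheduled visits, so a subject withdrawn for Grade 3 staining leaves the Visit 3 comparison, and the 24-hour revisit in Section 8.4 never enters it. In an illustrative simulation with 20% background Grade 1 in each sector and Grade 3 in one sector of 30% against 5% of subjects, the mean passed the 0.5 rule in about 100% of runs and the worst-sector grade in about 1%. The choice of summary clearly matters.

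Part of this stands: the listing's unit is unstated and no interval is planned. But the simulation compares two different endpoints, and the plan declared one of them openly in advance. A supportive worst-sector estimate with no margin would leave the decision exactly as it is. The missing rationale for 0.5 is not particular to staining, since no bound in Sections 2.1.1 or 2.1.2 has one. Section 11.1 says the protocol follows ISO 11980:2012; without that standard, one cannot tell whether it bears on the bound. A subject withdrawn after Visit 2 still counts in the Visit 2 tables, the adverse events and the discontinuations.

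**Conclusion.** No change to the plan is needed. Averaging does dilute staining in a single sector five-fold, and under the assumed 20% against 5% scenario the mean rule would almost certainly pass. But the mean grade is a declared and defensible endpoint, and the same scenario would appear as 24/120 against 3/60 in tables already planned by solution, as well as in adverse events and withdrawals. The remaining gap is one of detail: an interval about 10 points either side of the difference, and a phrase confirming that sector grades are counted. A competent analyst would supply both, and neither would alter the non-inferiority result.

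This rests on reading the Grade 2 or higher listing and the frequency tables as using recorded grades. The staining rates and SDs are assumptions, and the documents do not say whether staining will be localised.
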